Using the CCM model, One Hope has had many patients improve their health, including individuals who have been able to reduce or stop taking their diabetes medication. One Hope staff note that people participating in the diabetes program have changed their food- and physical activity-related behaviors and attitudes. Lowered blood sugar levels and improved diabetes self-maintenance have been reported anecdotally. One Hope conducted a preliminary analysis of patient medical records and found that CCM diabetes patients demonstrated statistically significant decreases in A1c values at months #5, 8, 11, 14, 18 and 22 after they joined One Hope’s program.¹⁰²

Our comparator choice will reduce the potential for biases and allow for direct comparisons. The two comparator sites are distinct in their diabetes management program models, thus allowing (after controlling for other factors) for direct comparison of the effects of the program on the primary and secondary outcomes. This choice of comparators will

PROTOCOL TITLE: Comparing Program Options for Latinos with Diabetes

reduce the potential for bias for the following reasons: 1.) The two comparators serve relatively similar populations in terms of socio-demographic attributes. 2.) Diabetes self-management program models in use at the two comparator sites have program attributes that are sufficiently distinct to allow contrast and comparison. And, 3.) Each of the comparator sites is implementing a program in a “real life” setting, thus providing the opportunity for a pragmatic assessment of the comparative effectiveness of the program models under externally valid and generalizable conditions.

2.3 Provide the scientific or scholarly background for, rationale for, and significance of the research based on the existing literature and how will it add to existing knowledge.

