9.0 Procedures Involved*

9.1 Describe and explain the study design.

This project adheres to PCORI methodological standards. Patient-reported outcomes measured with validated and reliable instruments will be the basis for us to compare the effectiveness of two distinct evidence-based models for culturally competent diabetes health promotion through research with two diabetes self-management programs that each currently serve a large Latino patient population from low-income households in Albuquerque, New Mexico. Data will be gathered at baseline, and 3, 6, and 12 months by paid PDCSs (PDCSs) from the target patient population who will be members of the research team. *A priori*, we believe patient populations for each program will be similar, yet we will compare sample characteristics and assess treatment differences after adjusting for possible population differences including the use of propensity scores in our statistical models to mitigate self-selection bias, possible confounding, and heterogeneity of treatment effects. Trickett's conceptualization of "cultural situated-ness" discussed above provides the theoretical framework for this study.^{37,38} We follow National Institutes of Health (NIH) standards for mixed method research set by Creswell and colleagues³⁹ in our "embedded mixed method" research approach, integrating data from quantitative and qualitative components of the study in an iterative fashion.³⁹ Our quasi-experimental research design with pre-/post-testing will accommodate the fact that we are working with existing programs at two sites and that we will recruit patients who enter those programs during the study.⁴⁰ Our sample size (N=240) and power estimates are based on realistic evaluation of effect size. We provide a detailed project timeline with specific deliverables that include scientific and engagement milestones. We have assembled a research team with the expertise and experience in patient-engaged research necessary to conduct the proposed study and we have an institutional infrastructure that supports our academic and community partnerships.

9.2 Provide a description of all research procedures being performed and when they are performed, including procedures being performed to monitor subjects for safety or minimize risks.

Data Collection.

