11.0 Data Management* and Confidentiality

11.1 *Describe the data analysis plan, including any statistical procedures.*

Descriptive statistics will be calculated to summarize patient characteristics. Means and standard deviations or medians and quartiles will be calculated for continuous variables and will be compared across site by ANOVA or Kruskal-Wallis test, depending on the distribution of the data. Frequencies and percentages will be calculated for categorical variables and will be compared with the chi-square test or Fisher's exact test, as appropriate. Significant differences will be noted and to adjust for possible confounding, those variables will be considered for inclusion as covariates in the analyses for the primary and secondary outcomes in addition to other clinically meaningful variables and their interactions. We expect patient characteristics to be similar across the two treatment sites; however, to control for potential differences in the populations, we will adjust for potential confounding covariates by using propensity scores to stratify subjects into groups based on the probability that they attended a particular treatment site given particular demographic characteristics including sex, age, primary language, level of education, nativity, and type of insurance. Patients will be grouped by quintile of propensity score for a total of five strata and each will be analyzed for the primary and secondary outcomes independently. Analyses will be performed in standard statistical software such as SAS 9.4, R 3.1, and/or Stata 14. Propensity score matching allows for causal inference in our non-experimental settings by selecting similar subsets of comparison units between treatment groups across a high-dimensional set of pretreatment characteristics.

We will complement our quantitative analyses by conducting a rigorous, disciplined, empirical analysis of data from key staff/provider interviews (Aim #1), patient/social support interviews and focus groups (Aims #1 & 2), and Patient Advisory Board interview transcripts.

PROTOCOL TITLE: Comparing Program Options for Latinos with Diabetes

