Hypothesized Effect Size for Intervention on Main Patient-Centered Outcome. We hypothesize that the CCM model, because following Trickett it is more effectively *situated* with patient culture and socio-economic context,^{37,38} will be superior to the DSMS in its ability to increase diabetes knowledge and patient activation, lower A1c, and improve depression scale scores and BMI among participants. Using the CCM model, One Hope has had many patients improve their health, including individuals who have been able to reduce or stop taking their diabetes medication. One Hope staff note that people participating in the diabetes program have changed their food- and physical activity-related behaviors and attitudes. Lowered blood sugar levels and improved diabetes self-maintenance have been reported anecdotally. One Hope conducted a preliminary analysis of patient medical records and found that CCM diabetes patients demonstrated statistically significant decreases in A1c values at months #5, 8, 11, 14, 18 and 22 after they joined One Hope's program.¹⁰²

The quantitative Primary Outcome for this study is improved patient capacity for diabetes self-management:

1.) Diabetes knowledge will be measured using the *DKQ summed score*. Hypothesis: The CCM model will result in a larger increase in DKQ summed scores from baseline to 6 months with a Cohen's f effect size (ES) = 0.09 as compared to the DSMS. Previously published studies evaluating culturally competent diabetes management programs report meaningful changes in DKQ summed scores with effect sizes of 0.03 to 0.16 in studies ranging in sample sizes per arm from 10 to 189.^{51,53,54,103}

2.) Patient activation will be measured using the *PAM-13 raw score*. Hypothesis: The CCM model will result in a larger increase in PAM-13 raw scores from baseline to 6 months with Cohen's f ES = 0.07 as compared to the DSMS. Previously published studies evaluating culturally competent diabetes management programs report changes in PAM-13 raw scores with meaningful effect sizes of 0.01 to 0.16 in studies ranging in sample size per arm from 26 to 133 (per Shah, Co-I [name], and colleagues¹⁰⁴).^{66,105-107}

The quantitative Secondary Outcome for this study is successful diabetes self-management as measured by improvement in A1c, BMI, and PHQ-9. Self-management will be measured through change in A1c, BMI, and depression index (PHQ-9).

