24.0 Local Number of Subjects

24.1 *Indicate the total number of subjects to be accrued locally.*

Local Comparator Sites: We will compare 2 diabetes self-management program models used by many Latino patients from low-income households in Albuquerque, New Mexico: 1) The Diabetes Self-Management Support Empowerment Model at the University of New Mexico Hospital and 2) The Chronic Care Model at One Hope Centro de Vida Health Center.

Subjects: We will recruit a total of 240 patient-social support pairs from the two program sites: patients (N=240: 120 at each site) and a corresponding social support of each enrolled patient (N=240 – 120 at each site). We will also recruit up to 6 staff and providers from each site each year to participate in interviews.

In addition, we will recruit the seven members of our Patient Advisory Board.

24.2 If applicable, distinguish between the number of subjects who are expected to be enrolled and screened, and the number of subjects needed to complete the research procedures (i.e., numbers of subjects excluding screen failures.)

Our experience with successful recruitment leads us to believe that we will be successful enrolling according to the plan we have laid out. Based on our experience working with this population in Albuquerque, our retention rates average 80-85%, which are consistent with other studies involving a similar population. To assure a conservative estimate, we estimated an attrition rate of 20% in our target recruitment.

Our previous study experience has demonstrated that we have the capacity to retain participants. We would like to emphasize our expertise and skill working with this patient population. The PI and the Co-PI have a strong record of working closely with individuals in the community and we have a cultural, linguistic and intellectual understanding of things that are important to patients and how to engage them. This makes a huge difference in the way that we, as researchers, interact with patient participants. Moreover, our PDCSs at both sites will be members of the patient population—Latino diabetes patients from low-income households. We believe that this will make a significant difference in the way that participants respond to and interact with our research project. These factors will assist us in retaining participants.

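### With one site per program model, the design can compare the two programs as delivered but not CCM and DSMS as models

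*Combined protocol and SAP*

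**What the plan says.** Section 24.1 names the first comparator as "The Diabetes Self-Management Support Empowerment Model at the University of New Mexico Hospital". The other comparator in that section, from a different organization, is listed as "2) The Chronic Care Model at One Hope Centro de Vida Health Center". It plans "patients (N=240: 120 at each site". Section 9.1 calls the design quasi-experimental, chosen to "accommodate the fact that we are working with existing programs at two sites".

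The documents describe the target of inference at two levels.

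- **Programs or sites.** Section 1.1 says two programs will be compared. The patients' question in section 2.3 asks which of two programs suits them best. In section 11.1 the exposure in the A1c model is treatment site, and the power analysis in section 11.2 is for site differences. Section 2.2 speaks of the program when it describes the comparator choice as "thus allowing (after controlling for other factors) for direct comparison of the effects of the program on the primary and secondary outcomes".
- **Models.** Section 1.1 gives the purpose as the comparative effectiveness of two evidence-based models. Section 2.2 promises a "pragmatic assessment of the comparative effectiveness of the program models under externally valid and generalizable conditions". Section 2.3 describes a direct comparison of evidence-based models, with implications for other Latino populations, other minority patients and other chronic conditions. Section 11.2 hypothesizes that the CCM model "will be superior to the DSMS in its ability to increase diabetes knowledge and patient activation", and words each outcome hypothesis as an effect of the CCM model.

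No section says that model and site coincide, or limits the inference to these two programs.

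**The concern.** When each model runs at one site, everything particular to that site travels with the model. A difference in knowledge or activation scores could come from the model, from the way one organization runs it, or from features of that organization that have nothing to do with it. The data cannot distinguish these.

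The plan offers a remedy only for differences between patients. Its standard errors contain patient variation and no variation between sites running the same model. A significant result could then be read as a reason to adopt CCM elsewhere, when what it would show is that One Hope's program and CDE-UNMH's program gave different results.

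**Working it through.** **1. The plan's own figures.** Section 11.2 gives, for the DKQ, a difference of 2.2, SD 3.8, 96 per site, alpha 0.025 two-sided and power 96%.

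- Standard error = 3.8 × √(2/96) = 0.548.
- 2.2 / 0.548 = 4.01, and 4.01 − 2.24 = 1.77, so power = Φ(1.77) = 96.2%. This agrees.
- Recruitment: 96 / (1 − 0.20) = 120 per site. This agrees.

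The DKQ figure is recovered by treating patients as independent, with no between-site term. (Section 11.2 states both 0.0125 and 0.025 for the primary outcomes. The PAM-13 power of 85% corresponds to 0.0125; at 0.025 it would be about 90%. That is a separate matter. The illustration below uses 0.025, the level attached to the primary power figures.)

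**2. Aliasing.** There are two sites and two model means, so the degrees of freedom for site within model are 2 − 2 = 0. The model and site indicators are the same column of the design matrix. This needs no assumption.

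**3. Does any planned adjustment break it?**

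- The propensity strata in section 11.1 use sex, age, primary language, education, nativity and insurance. All are patient attributes.
- The regression covariates in sections 11.1 and 11.2 add social-support, knowledge, hair cortisol and CAHPS-CC measures. CAHPS-CC does bear on the program, but section 9.2 collects it only at 3, 6 and 12 months, so it lies downstream of site and cannot separate site from model.

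**4. Illustration of size for a model-level claim.** The ICC between sites running the same model is assumed; the documents give none and this design cannot estimate it. Sites are treated as random draws, and the plan's SD as the total SD. Design effect DE = 1 + 95 × ICC. True type I error = 2 × [1 − Φ(2.241 / √DE)].

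| ICC (assumed) | DE | Type I error at nominal 0.025 |
|---|---|---|
| 0 | 1.00 | 2.5% |
| 0.005 | 1.475 | 6.5% |
| 0.01 | 1.95 | 10.9% |
| 0.02 | 2.90 | 18.8% |
| 0.05 | 5.75 | 35.0% |

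**5. Would more patients help?** As the number per site grows without limit, the standard error of the model contrast falls only to SD × √(2 × ICC). For the DKQ at ICC 0.01 that is 3.8 × √0.02 = 0.54, about the same as the 0.548 the plan assumes in total with 96 per site. Enrolling more patients at the same two sites does not solve the problem.

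**The case against.** The strongest reply is that the analysis is already a comparison of two programs. The exposure is treatment site, the power is for site differences, and the patients' question is about programs. That stands: the contrast of programs as delivered is a legitimate estimand, and no analysis has to change.

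Four stronger readings are tempting, and the documents do not support them.

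- A reader might infer that the protocol commits itself to concluding that CCM is superior. Section 11.2 states a hypothesis, the type I error is two-sided, and no rule is set for interpreting a significant result.
- A reader might take the comparator sentence in section 2.2 as the model-level claim. It refers to effects of the program. The overreach lies in the later sentence on program models and generalizable conditions, and in sections 2.3 and 11.2.
- A reader might treat One Hope's community staffing, facility and access regardless of ability to pay as pure site effects. Section 2.2 lists them under the implementation of the CCM, and improved access is one of the six CCM domains. The fair criticism is that the protocol never says which features belong to the model and which to the site.
- A reader might say that the error rate is simply far above nominal. It equals nominal at ICC 0, and the inflation applies only if the two sites stand for a population of sites, which the protocol does not define.

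Nor does the propensity-score text in section 11.1 claim to separate site from model. It concerns similarity of patients on pretreatment characteristics.

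None of this supplies the missing acknowledgement. The model-level and generalizability wording remains without support in the design.

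**Conclusion.** The point holds as a limit on inference. That model and site are fully aliased follows from the design alone. The difference between One Hope's program and CDE-UNMH's program is estimable, subject to patient-level confounding, and aliasing does not inflate its type I error. Attribution of that difference to CCM versus DSMS as models, and its extension to other settings, populations or conditions, is not supported.

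The error rates of 2.5% to 35% illustrate what a model-level reading could cost over assumed ICCs of 0 to 0.05. They are not estimates for this study.

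**What to change.** In sections 1.1, 2.2, 2.3 and 11.2:

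- define the estimand as One Hope's program versus CDE-UNMH's program, each as delivered;
- state that intervals and p-values are conditional on these two sites;
- state as a limitation that model and site coincide, and that the protocol does not separate the One Hope features that belong to the CCM from those specific to the site;
- remove or qualify the attribution of differences to CCM versus DSMS as models, and the claim of generalizable conditions.

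The hypotheses can stay if they name the programs. No data collection, sample size or analysis changes. The cost is a narrower stated conclusion, though one that still answers the patients' question of which of the two programs serves them better.

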3.0 Inclusion and Exclusion Criteria*

3.1 Describe how you individuals will be screened for eligibility.

Staff & Providers (n=36):

PROTOCOL TITLE: Comparing Program Options for Latinos with Diabetes

Our Program Liaison at each site will identify up to 6 key program staff and/or providers per site each year for assessment interviews that will contribute to our understanding of the program sites. Our Research Manager will contact them using an IRB-approved script to invite them to participate and schedule appointments with those interested. At the appointment, the Research Manager will ask them to sign the consent and complete the contact portion of the Data Sheet only, and then will conduct the interview.

Patient (n=240) & Social support (n=240) participants:

All patient participants will be individuals who have been identified by a provider as having pre-diabetes (A1c 5.7-6.4) or diabetes (A1c 6.5 or above) and are newly entering one of the two programs involved in this study (CDE-UNMH or One Hope). We will not enroll individuals who have already been participating at the sites as this would not allow us to gather data in line with our data collection protocol (baseline, 3, 6, and 12 months).

At CDE-UNMH, when patients register for the program, CDE-UNMH staff will tell them about the study using an IRB-approved script and a flyer with pull-off tabs will be posted in the CDE office. An invitation with further detail about the research and contact information for our PDCSs--the *Patient Data Collection Specialists* (PDCSs)--will be sent in a mailing that all new patients receive from CDE-UNMH with their class schedule confirmation and logistics. A staff person at CDE-UNMH or a member of the research team will phone new participants to tell them about the study. For those who indicate that they are interested, the staff person will ask the patient's permission to release their name and contact information to our PDCSs. If the patient agrees, a member of the research team will contact the patient. Interested patients can also contact the PDCS using the information on the mailing. For all interested patient participants, the PDCS will screen them per our recruitment criteria.

At One Hope, participants will be identified in three ways: 1) New patients who call the clinic and indicate that they need to see a provider specifically about diabetes will be told about the study using an approved script, 2) Every patient seen at the clinic has an exit interview (*salida*) conducted by a Community Health Worker. For patients who have been told by their provider to have their A1c checked or that they have a diagnosis of diabetes or prediabetes, they will be told about the study using an approved script, and 3) Flyers about the study will be posted in the One Hope waiting room. For those who indicate interest in participating, a PDCS will contact them, inform them about the research per IRB requirements, and screen them for eligibility. For those who are eligible, the PDCS will schedule an appointment to consent them and gather baseline data.

PROTOCOL TITLE: Comparing Program Options for Latinos with Diabetes

At both sites, interested patients who qualify will provide contact information for a person that they identify from their social network (family or friend) whom they consider as their primary “social support.” A member of the research team will contact the social support, provide them with information about the study, and invite them to participate. The PDCS will schedule an appointment with supports who are interested.

At the appointment, the PDCS will ask all participants to sign the consent, collect the information in the Participant Data Sheet, and collect responses to the baseline survey questions. The PDCS will also obtain a blood sample, measure BMI, and gather a hair sample for the patient only.

Subset of Patient and Social support Participants for Interviews (72) and Focus Groups (72): At each of the sites, the PDCS will identify a convenience sample of interviewees and focus group participants from those already recruited to be in the study and invite them to participate. Our Research Manager will contact those interested to schedule.

3.2 *Describe the criteria that define who will be included or excluded in your final study sample.*

Staff & Providers will be individuals who work at one of the two sites.

Patients will be screened by a member of the research team. Patients will be adults (men and women) who have been identified by a provider as having pre-diabetes (A1c 5.7-6.4) or diabetes (A1c 6.5 or above) and: 1.) Enter one of the two diabetes programs during the study; 2.) Self-identify as “Latino;” 3.) Can identify a social support or key member of their social network who will agree to participate with them; 4.) Are not pregnant (participants who become pregnant during the study will be excluded); and 5.) Have household income 250% of the FPL or below. Participants who become pregnant during the study will be excluded. Additionally, we have discovered that there is a difference between the A1c test that CTSC runs and the test run at Quest or TriCore. The test CTSC uses is reliably .2 lower and this is cited in the literature. Therefore, it is appropriate for us to enroll individuals who have a test at another lab that shows them to be pre-diabetic (A1c 5.7-6.4) even if our baseline lab comes back lower (5.5-6.2). However, any individual whose blood gathered by our data collectors at baseline returns with an A1c below 5.5 will be disenrolled.

Social supports will be adult individuals who are identified by the patient participants and who agree to participate.

Advisory Board Members will be seven members of our Project Patient Advisory Board.

PROTOCOL TITLE: Comparing Program Options for Latinos with Diabetes

3.3 Indicate specifically whether you will include or exclude each of the following special populations: (You may not include members of the above populations as subjects in your research unless you indicate this in your inclusion criteria.)

1. *Adults unable to consent*
2. *Individuals who are not yet adults (infants, children, teenagers)*
3. *Pregnant women*
4. *Prisoners*

We will not recruit:

- Adults unable to consent
- Individuals who are not yet adults (infants, children, teenagers)
- Prisoners
- Pregnant women.

At enrollment, we will screen to specifically exclude participants who are pregnant. There is no risk to a pregnant woman or a fetus entailed in participation in this study because the study only involves data collection from individuals who have been instructed to participate in a diabetes self-management program by their provider. However, we will exclude pregnant individuals because we recognize that pregnancy could impact outcomes in a way that will influence our scientific analysis of diabetes self-management. At each data collection point, we will ask female participants if they are pregnant. If we discover that a participant has become pregnant during the course of the study, they will be given an end-of-study visit to end their participation and their data will be excluded. Co-I [name] will give them a referral to the UNM specialty prenatal clinic for high-risk pregnancies. It will be made clear to them that ending their participation in our study does not affect their ability to continue participating in the diabetes program that they attend.

This study involves regular screening for A1c levels. For A1c (>10), we will notify the participant's PCP. If we see a lab value that could indicate an emergency (Glucose > 400 mg/dl, < 60 mg/dl), we will contact the participant to make sure they are aware of their A1c status and that they are receiving appropriate care. If the participant would like more information about what to do, Co-Investigator [name] will advise them. For women with an elevated A1c, when we contact them to tell them about their elevated test results we will inquire whether or not they are or think they might have become pregnant since entering the study.

PROTOCOL TITLE: Comparing Program Options for Latinos with Diabetes

If so, Co-Investigator [name] will provide them with a referral to UNM's High Risk Obstetrics Clinic.

